4.2. Part 2 Study Population

Up to approximately 40 participants from Part 1 of the study will be eligible to enroll in Part 2 of the study (Optional OLE). Enrollment in Part 2 is optional for the participant, and at the discretion of the investigator.

4.2.1. Inclusion Criteria - Part 2 (Optional OLE)

The OLE is optional for participants who complete Part 1 of the study. Participants who complete Week 97 of Part 1 of the study are eligible for continued treatment with AL001, provided that all of the following criteria are met:

1. Participant is willing and able to give informed consent to continue treatment with AL001. If the study participant is not competent, a legally authorized representative must provide informed consent on their behalf, and the participant must provide assent, in accordance with the local regulations, guidelines, and institutional review board (IRB) or independent ethics committee (IEC).
2. Is willing and has the ability to comply with OLE requirements, in the opinion of the investigator.
3. Has availability of a person (“study partner”) who can continue to assist with assessments throughout the OLE evaluation period. The study partner must have frequent and sufficient contact with the participant (at least 5 hours per week of in-person contact), have the ability to provide accurate information regarding the participant’s cognitive and functional abilities as well as their health throughout the study, agree to provide information at site visits that require partner input for COA completion, and sign the necessary consent form. (Note: asymptomatic participants require the study partner at the COA visits only; symptomatic participants require the study partner at each visit).
 - The study partner must have sufficient cognitive capacity to accurately report upon the participant’s behavior, cognitive, and functional abilities. The study partner should be in sufficiently good general health to have a high likelihood of maintaining the same level of interaction with the participant, and participation in study procedures throughout the study duration.
 - The Part 2 study partner can be the same individual as in Part 1, or it can be a different individual, but the same Part 2 study partner should participate throughout the duration of Part 2. If a change in study partner during Part 2 is necessary, the Medical Monitor must be contacted.

4.2.2. Exclusion Criteria - Part 2 (Optional OLE)

Part 1 participants are not eligible for continued treatment with AL001 OLE if any of the following apply:

1. Part 1 participant has been admitted to a skilled nursing facility, convalescent home, or long-term care facility at screening and requires continuous nursing care (i.e., >3 months).
2. Part 1 participant has a CDR[®] plus NACC FTLD global score >2 during Part 1.
3. Part 1 participant has a medical condition or extenuating circumstance that, in the opinion of the investigator, continued treatment with AL001 at the conclusion of Part 1 is not beneficial or safe for the participant.

4.3. Withdrawal of Participants from Study Drug and/or the Study

The duration of the study is defined for each participant as the date signed written informed consent is provided through the End of Study Visit (Part 1 or Part 2)/Safety Follow-up Visit, whichever is later. A Study Discontinuation section of the electronic case report form (eCRF) must be completed for all enrolled participants only.

4.3.1. Part 1 (Treatment Period)

4.3.1.1. Withdrawal from Study Drug (Part1)

A participant may be discontinued from study drug at any time if the participant or the investigator feels that it is not in the participant's best interest to continue. The following is a list of possible reasons for study drug discontinuation:

1. Participant is noncompliant with the protocol
2. Participant is lost to follow-up
3. Participant withdraws consent
4. Participant has a serious or intolerable AE that, in the investigator' opinion, requires withdrawal from the study drug
5. Serum aminotransferase levels (ALT or AST) $>3 \times$ ULN AND total bilirubin $>2 \times$ ULN without an alternative explanation
6. Anaphylaxis
7. Infusion-related or injection-related reaction despite adequate premedication for an initial occurrence of a moderate to severe infusion-related reaction ([Section 5.1.2](#)) or if the participant experiences any of the following events: mucosal tissue involvement, airway compromise, or symptomatic hypotension with systolic blood pressure <90 mm Hg measured in the supine position
8. Occurrence of an intercurrent illness that, in the investigator's opinion, will affect assessments of clinical status or safety to a significant degree
9. Use of a nonpermitted concomitant medication per [Section 4.1.2](#) (as appropriate)
10. Pregnancy
11. Discretion of the investigator

If a participant is withdrawn from study drug due to an AE or SAE, the participant will be followed up by the investigator until the abnormal parameter or symptom has resolved or stabilized (if applicable). The investigator has the responsibility for all decisions regarding participant safety. It is recommended that the investigator consult with the Medical Monitor prior to removing the participant from study drug for any reason except participant withdrawal of consent and in case of medical emergency. If a participant is discontinued because of an AE or SAE, the event will be followed up until it is resolved. Any participant may withdraw his or her consent at any time.

All participants who discontinue study drug prior to the completion of the Part 1 96-week treatment period should be encouraged to complete all remaining scheduled assessment visits through the Part 1 treatment period (Week 97). Study staff will follow-up to aid in this goal.

The reason for the participant's early discontinuation of study drug will be specified in the participant's source documents and on the eCRF. A Part 1 End of Treatment (EOT) visit will be completed by participants who discontinue the study drug but remain in the study and continue to perform assessments. Part 1 EOT assessments should be completed as soon as possible after the decision is made. A Safety Follow-Up visit will be performed 10 weeks after their last study drug administration. The Safety Follow-up visit may be substituted by a scheduled visit if it occurs within the same window.

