1.1.3. Sortilin and AL001

Human and mouse genetic studies identified the transmembrane receptor Sortilin, encoded by the *Sortilin 1* gene, as the major negative regulator of PGRN levels in plasma and the brain (Hu 2010; Carrasquillo 2010). Sortilin binds PGRN and targets it for lysosomal degradation resulting in a reduction of extracellular PGRN. Blocking Sortilin/PGRN interactions, therefore, provides a therapeutic strategy for sustaining PGRN levels in the central nervous system (CNS) and minimizing progression of FTD-associated dementias.

AL001 is a recombinant humanized monoclonal antibody that binds specifically to Sortilin and is being studied for the treatment of carriers of *GRN* mutations causative of FTD and carriers of *C9orf72* hexanucleotide repeat expansion mutation causative of FTD.

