4.1.2. Exclusion Criteria - Part 1 (Treatment Period)

Prospective participants who meet any of the following criteria during the pre-study evaluation will be excluded from enrolling in the study:

1. History of severe allergic, anaphylactic, or other hypersensitivity reactions to chimeric, human, or humanized antibodies or fusion proteins.
2. History of substance use disorder (drug or alcohol) within 2 years prior to the first study drug administration, with the exception of nicotine, as defined by the Diagnostic and Statistical Manual of Mental Disorders, fifth edition criteria ([American Psychiatric Association 2013](#)).

3. Current acute illness or active infection requiring oral or IV antibiotics within 30 days prior to the first study drug administration that may affect safety assessments.
4. History of surgery or hospitalization during the 30 days prior to first study drug administration.
5. History of cancer within the last 5 years with the exception of basal cell or squamous cell carcinoma.
6. History or presence of intracranial tumor that is clinically relevant (e.g., glioma, cerebral metastasis).
7. Positive for hepatitis B surface antigen, hepatitis C virus antibodies, or human immunodeficiency virus-1 and -2 antibodies or antigen, or history of spirochetal infection of the CNS (e.g., syphilis or borreliosis).
8. Significant kidney disease as indicated by a screening creatinine clearance <30 mL/min as calculated by the central laboratory using the Cockcroft-Gault formula, which remains <30 mL/min if retested.
9. Impaired hepatic function as indicated by screening aspartate aminotransferase (AST) or alanine aminotransferase (ALT) $\geq 2.5 \times$ the upper limit of normal (ULN) or total bilirubin $\geq 1.5 \times$ ULN, which remains above either of these limits if retested or other abnormalities in synthetic function that are clinically significant. Note: Participants with Gilbert's syndrome are eligible to participate if approved by the Medical Monitor.
10. Unstable or clinically significant cardiovascular disease (e.g., myocardial infarction, angina pectoris, New York Heart Association Class III or more cardiac failure) within the last 2 years.
11. Uncontrolled hypertension, defined as an average systolic blood pressure ≥ 150 mmHg or an average diastolic blood pressure ≥ 95 mmHg, in an individual with hypertension.

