4.4. Part 2 (Optional OLE)

4.4.1. Criteria for Withdrawal of Participants in Part 2

A participant may be discontinued from Part 2 of the study (including study drug and all assessments) at any time if the participant or the investigator feels that it is not in the participant's best interest to continue. The following is a list of possible reasons for Part 2 study discontinuation:

1. Long-term placement in a skilled nursing convalescent home, or long-term care facility at screening and requires continuous nursing care. (i.e., >3 months)
2. If, in the opinion of the investigator and Alector, they are unable to follow protocol procedures

3. If they develop intercurrent illness that would confound the interpretation of safety and efficacy data
4. CDR® plus NACC FTLD global score >2 during Part 2
5. AL001 is commercially available in the country where the participant is being treated
6. Participant withdrawal of consent
7. Lost to follow-up
8. Discretion of the investigator
9. Administrative or other reasons (e.g., premature termination of the study by Alector)
10. Participant is noncompliant with the protocol
11. Participant has a serious or intolerable AE that, in the investigator's opinion, requires withdrawal from the study drug
12. Serum aminotransferase levels (ALT or AST) $>3 \times$ ULN AND total bilirubin $>2 \times$ ULN without an alternative explanation
13. Anaphylaxis
14. Infusion-related or injection-related reaction despite adequate premedication for an initial occurrence of a moderate to severe infusion-related reaction ([Section 5.1.2](#)) or if the participant experiences any of the following events: mucosal tissue involvement, airway compromise, or symptomatic hypotension with systolic blood pressure <90 mm Hg measured in the supine position
15. Occurrence of an intercurrent illness that, in the investigator's opinion, will affect assessments of clinical status or safety to a significant degree
16. Use of a nonpermitted concomitant medication per [Section 4.1.2](#) (as appropriate)
17. Pregnancy

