5.1.2. Infusion-Related and Injection-Related Reactions

All participants will be monitored for infusion-related reactions or injection-related reactions during the infusion/injection and immediately afterwards for at least 60 minutes.

Injection-related reactions can be localized at the site of the injection or systemic and should be treated per institutional guidelines. If a participant experiences a mild infusion-related reaction,

the infusion should be halted. Once the reaction has resolved, the infusion rate will be resumed at half the most recently used rate (e.g., from 60 mL/hr [1.0 mL/min] to 30 mL/hr [0.5 mL/min]). The infusion should be stopped immediately for any participant who experiences a moderate to severe infusion-related reaction (e.g., fever or chills), and the participant should receive aggressive symptomatic treatment. The infusion should not be restarted before all symptoms have disappeared, and then it should be restarted at half of the initial rate. The infusion should not be resumed if there is a second occurrence or if the participant experiences any of the following events: mucosal tissue involvement, airway compromise, or symptomatic hypotension with systolic blood pressure <90 mm Hg measured in the supine position.

In addition, in the event of an infusion-related reaction, a sample of blood should be obtained for PK serum and ADA assessment of AL001, and testing should be performed for C-reactive protein, tryptase, and Interleukin 6 (IL-6). Further details regarding infusion-related reactions are provided in the IB.

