7.10. Anaphylaxis

Signs or symptoms of anaphylaxis will be carefully monitored and treated according to institutional guidelines. Emergency crash cart equipment and medications, including multiple doses of epinephrine, pressors, and bronchodilators, will be available at all times during the infusion portions of the study.

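### Anaphylaxis, severe infusion reactions and unexplained ALT/AST-plus-bilirubin elevation are listed only as possible reasons to stop AL001; the protocol should require a permanent stop

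*Protocol*

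**What the plan says.** Protocol Section 4.3.1.1 governs stopping study drug in Part 1. Its opening sentence is permissive: a participant may be taken off drug if the participant or the investigator thinks that continuing is against the participant's interest. The criteria are then introduced with "The following is a list of possible reasons for study drug discontinuation". Item 5 is ALT or AST above 3×ULN together with total bilirubin above 2×ULN and no other explanation. Item 6 is anaphylaxis. Item 7 covers infusion-related or injection-related reactions, including any with "mucosal tissue involvement, airway compromise, or symptomatic hypotension with systolic blood pressure <90 mm Hg measured in the supine position". Item 11, in the same list, is the investigator's discretion.

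Section 4.4.1 does the same for Part 2. It uses the same permissive verb, introduces the list with "The following is a list of possible reasons for Part 2 study discontinuation", and places the three events at items 12 to 14.

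Two other sections deal with reactions to the infusion. Section 5.1.2 says "The infusion should not be resumed if there is a second occurrence or if the participant experiences any of the following events", and then names the same three features as item 7. Section 7.10 says "Signs or symptoms of anaphylaxis will be carefully monitored and treated according to institutional guidelines" and adds the emergency equipment that must be at hand.

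**The concern.** Safety is the primary objective of both parts, and Section 1.3.1 names severe anaphylactic reactions as a risk of the drug class. These are the events for which one expects a protocol to remove discretion.

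For anaphylaxis, the entry rule is stricter than the continuation rule. Exclusion 1 in Section 4.1.2 bars anyone with "History of severe allergic, anaphylactic, or other hypersensitivity reactions to chimeric, human, or humanized antibodies or fusion proteins", and Section 1.1.3 states that "AL001 is a recombinant humanized monoclonal antibody that binds specifically to Sortilin". A participant who reacted in this way to AL001 would fail screening if screened afresh, yet the text does not require that participant to come off drug. The liver criteria show a similar contrast. Exclusion 9 bars entry at AST or ALT of 2.5×ULN or more, or total bilirubin of 1.5×ULN or more, if confirmed on any retest. The more serious combined pattern on treatment carries no required stop.

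At stake is whether about 13 sites, reading this text, would all stop drug after such an event. A site that gave the next 60 mg/kg infusion would not be departing from either withdrawal list.

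**Working it through.** No arithmetic bears on this point. The check is whether any section turns the permissive lists into a required permanent stop.

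| Protocol text | What it governs | Bars the next dose? |
|---|---|---|
| 4.3.1.1, items 5 to 7 (Part 1) | Reasons for which drug may be stopped | No, permissive |
| 4.4.1, items 12 to 14 (Part 2) | Reasons for which participation may end | No, permissive |
| 5.1.2 | Halting, slowing or not resuming the current infusion | No, silent on the next visit; does not address the liver criterion |
| 7.10 | Monitoring, treatment, equipment | No |
| 4.1.2, exclusions 1 and 9 | Pre-study evaluation | No, entry only |
| 4.2.2, item 3 | OLE entry, if in the investigator's opinion "continued treatment with AL001 at the conclusion of Part 1 is not beneficial or safe for the participant" | Only by judgement, and only at that transition |
| Appendix 3, home dosing | Medical Monitor approval and site confirmation; refers to 5.1.2 for reactions | No event-specific bar |
| 12.1, iDMC | Review after the first 6 participants reach about 12 weeks, then every 6 months | No, not a per-dose check |

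The SAP tabulates adverse events leading to drug discontinuation (Section 6.1.5) and contains no stopping rule.

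The count is therefore 0 of 2 withdrawal lists with mandatory wording, and 0 other available sections that require a permanent stop for any of the three events.

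Section 5.1.2 cannot be read as a permanent stop by implication. It allows the infusion to be restarted, at half the initial rate, once the symptoms of a moderate to severe reaction have cleared. Item 7 refers to a reaction that occurs despite premedication given because of an earlier one, which presupposes further dosing after a first reaction.

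The protocol does use firm wording elsewhere:

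- Section 7.12 says that a participant who becomes pregnant must be told to stop drug.
- Section 3.1 and the synopsis say that OLE participants will be discontinued for four reasons: long-term nursing placement, a CDR plus NACC FTLD global score above 2, inability to follow procedures, and confounding intercurrent illness.

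All four OLE reasons, and pregnancy, reappear in Section 4.4.1 as possible reasons only. So Section 4.4.1 disagrees with Section 3.1 on four items, and a dementia rating above 2 has a firmer stop in Section 3.1 than anaphylaxis has anywhere.

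**The case against.** The best reply is that the list is a catalogue of reasons, one of which is then recorded on the eCRF, and was never meant to make each item optional. It includes withdrawal of consent and loss to follow-up, which nobody would call discretionary, and pregnancy, which Section 7.12 makes mandatory. Where judgement is intended, the item says so: items 4 and 8 refer to the investigator's opinion, and item 9 is to be applied as appropriate. Items 5 and 6 carry no such qualifier, and Section 4.4.1 is headed as criteria. This stands as evidence that firm stops may have been intended. It does not change the governing sentences, which are permissive in both sections.

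A second reply is that Section 1.3.4 assigns toxicity management partly to the Investigator's Brochure, and Sections 5.1.2 and 7.9 refer there for infusion reactions. The brochure was not available, nor was one stretch of protocol text next to Section 1.3.2. Either might contain a stop. The point is therefore limited to the protocol text that could be read.

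A third is that safeguards exist: the investigator is responsible for safety decisions, SAEs reach the sponsor within 24 hours (Section 7.6), and adverse events are reviewed at every visit. These make re-dosing unlikely but do not prohibit it.

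A reader might go further and size the risk by counting infusions. After a reaction at infusion 2 of 25, 25 − 2 = 23 Part 1 infusions remain. That is a ceiling on what the wording leaves open. It assumes an investigator who re-doses every time, and nothing in the documents suggests that. A reader might also note that (37 − 25)/4 − 1 = 2 infusions, at Weeks 29 and 33, fall between the scheduled chemistry draws at Weeks 25 and 37. That count mainly reflects the 12-week testing interval: an abnormality arising between draws would go just as unseen under mandatory wording, and Section 7.3 follow-up or an unscheduled visit could detect it sooner. Neither count measures risk.

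**Conclusion.** The concern holds as a gap in wording. Anaphylaxis, infusion reactions with the three severe features, and the unexplained combined liver pattern are events for which drug may be stopped, and no section that could be read bars the next dose. It is best treated as a cheap improvement to patient safety.

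The documents do not support the stronger inference that the sponsor intends re-dosing after these events, or that participants face a quantifiable excess risk. Section 1.3.2 reports no serious adverse drug reactions to date, and most investigators would probably stop. The conclusion assumes that neither the Investigator's Brochure nor the unavailable protocol text contains a binding stop. If one does, the protocol still needs to state it or point to it from the withdrawal sections.

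The mismatch between Sections 4.4.1 and 3.1 is minor, because Section 3.1 and the synopsis already state the firm rule.

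**What to change.** Divide the lists in Sections 4.3.1.1 and 4.4.1 into mandatory and discretionary items. The mandatory part, identical in both, should say that study drug must be permanently discontinued for:

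- anaphylaxis;
- an infusion-related or injection-related reaction, as described in Section 5.1.2, with mucosal tissue involvement, airway compromise, or symptomatic hypotension with supine systolic pressure below 90 mm Hg;
- ALT or AST above 3×ULN with total bilirubin above 2×ULN and no alternative explanation;
- pregnancy, to match Section 7.12.

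Keep the tie to an infusion or injection reaction in the second item. Without it, an unrelated hypotensive episode weeks after a dose would force a permanent stop. The third item still leaves the investigator to judge whether another cause explains the liver tests. Judgement-based items such as noncompliance and investigator discretion stay discretionary.

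As a minor alignment, make Section 4.4.1 agree with all four OLE triggers in Section 3.1 and the synopsis, or cross-refer to Section 3.1. Aligning only the two objective triggers would leave the mismatch in place for the other two.

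The cost is wording in the next amendment and a small loss of investigator discretion. Part 1 participants who stop drug are already encouraged to complete their remaining assessments. In Part 2 a stop leads to the End of Study visit, as it does now. No new visit, assessment or SAP change is needed.

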4.3.2. Withdrawal From Study (Part 1)

A participant may be discontinued from the study (including study drug and all assessments) at any time if the participant or the investigator feels that it is not in the participant's best interest to continue. The following is a list of possible reasons for study discontinuation:

1. Participant withdrawal of consent
2. Lost to follow-up
3. Discretion of the investigator
4. Administrative or other reasons (e.g., premature termination of the study by Alector)

All Part 1 participants who discontinue the study drug and all assessments prior to the scheduled Week 97 visit should be encouraged to return to the site for a Part 1 EOS visit. Part 1 EOS assessments should be completed as soon as possible after the decision is made. A Safety Follow-Up visit will be performed 10 weeks after the participant's last study drug administration. Reasonable attempts will be made by the investigator to obtain reasons for participant withdrawals (e.g., 2 documented telephone calls on different days, followed by 1 registered letter). The reason for the participant's withdrawal from the study will be specified in the participant's source documents and in the eCRF.

